8. ADVERSE EVENTS, RISKS, AND BENEFITS

8.1. Potential Benefits of treatment

Based on animal efficacy studies, it is expected that EIDD-2801 will be active against SARS-CoV-2 infection in humans. This study will examine virologic responses to treatment with EIDD-2801 and is not powered to detect clinical outcomes. However, clinical improvement will be recorded for secondary/exploratory analysis.

8.2. Potential benefits of clinical monitoring

Benefits of participation in this study include the increased clinical monitoring of study participants. Intensive virology testing will be conducted.

8.3. Potential risks

The AE profile for EIDD-2801 is preliminary and derives from a Phase 1 study that is ongoing. Thus far, AE that were determined to be attributable to EIDD-2801 include insomnia, headaches, nausea, vomiting, abdominal pain, and loose stools (*see* the EIDD-2801 Investigator's Brochure, V3.0, 2020).

Gastrointestinal events and liver enzymes will also be monitored.

8.4. Alternatives

The alternative to participation in this study is routine care and monitoring of COVID-19, receipt of a SOC treatment for SARS-CoV-2 infection if available, or participation in a different clinical trial, if available.

8.5. Definitions

8.5.1. Adverse Event

Adverse event is defined as any undesirable sign, symptom or medical condition occurring after starting the study drug (or therapy/intervention) even if the event is not considered to be related to the study. An undesirable medical condition can be symptoms (e.g., nausea, chest pain), signs (e.g., tachycardia, enlarged liver) or the abnormal results of an investigation (e.g., laboratory findings, electrocardiogram). Medical conditions/diseases present before starting the study treatment are only considered AEs if they worsen after starting the study treatment (any procedures specified in the protocol). Adverse events occurring before starting the study treatment but after signing the informed consent form will not be recorded. Abnormal laboratory values or test results constitute AEs only if they induce clinical signs or symptoms or require investigation or therapy (i.e., are considered to be clinically significant).

This study will use the descriptions and grading scales found in the DAIDS Adverse Event Grading Scale for AE reporting.

Version: 7.0 18 May 2021

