1.2. Primary Safety Objective

Primary Safety Objective:

To evaluate the safety of treatment with EIDD-2801 in participants diagnosed with COVID-19

Primary Safety Endpoints:

- 1. Adverse events (AEs)
- 2. Serious adverse events (SAE)
- 3. Physical examination including vital signs
- 4. Safety laboratory assessments:
 - complete blood counts (CBC) with differentials
 - decrease in hemoglobin (Hgb) by >1 g/dL, or to <9 g/dL
 - decrease in platelet count by $50,000/\mu$ L, or to $<75,000/\mu$ L
 - comprehensive metabolic panels (CMP) including liver function tests
 - increase in aspartate aminotransferase (AST), alanine aminotransferase (ALT), amylase, or lipase to ≥3x the upper limit of normal (ULN)
 - urinalysis
- 5. Electrocardiograms (ECGs)

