6.2.6. Analysis of Adverse Event Data

Analysis of AE data will primarily be descriptive based on the DAIDS table for Grading the Severity of Adult and Pediatric Adverse Events, July 2017, version 2.1. Adverse events will be coded using the Medical Dictionary for Regulatory Activities (MedDRA). An AE is considered treatment-emergent if it begins or worsens in severity after the first dose of randomized study drug. The number and percentage of participants with treatment-emergent AEs will be tabulated by system organ class (SOC) and preferred term. Additional AE summaries will be provided by severity, drug related AEs, AEs leading to study drug discontinuation, and serious AEs.

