8.10.2. Laboratory Test Abnormalities

Laboratory abnormalities present at the screening visit will be recorded as pre-treatment signs and symptoms. After study treatment administration, all grade 3 and 4 clinical laboratory results that represent an increase in severity from baseline will be reported as AEs. A grade 1 or 2 clinical laboratory abnormality should be reported as an AE only if it is considered clinically significant by the investigator.

In addition, the following laboratory abnormalities should also be captured on the AE CRF page as appropriate:

- Any laboratory test result that is clinically significant or meets the definition of an SAE
- Any laboratory abnormality that required the participant to have the investigational product discontinued or interrupted
- Any laboratory abnormality that required the participant to receive specific corrective therapy

It is expected that wherever possible, the clinical, rather than the laboratory term would be used by the reporting investigator (e.g., anemia versus low hemoglobin value).

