9.2. Stopping Criteria for the Study

The study enrollment and dosing will be stopped, and an ad hoc review will be performed if any of the specific following events occur or, if in the judgment of the study physician, participant safety is at risk of being compromised:

- I. Unexpected death of a dosed participant.
- II. Occurrence of a life-threatening allergic/hypersensitivity reaction (anaphylaxis), manifested by bronchospasm with or without urticaria or angioedema requiring hemodynamic support with pressor medications or mechanical ventilation.
- III. A trend of unexpected SAEs related to the study product.
- IV. Two participants with a Grade 3 or higher lab toxicity for the same parameter associated with the study product.
- V. An overall pattern of symptomatic, clinical, or laboratory events that the SRC considers associated with study product and that may appear minor in terms of individual events but that collectively may represent a serious potential concern for safety.
- VI. Any other event(s) which is considered to be a SAE in the good clinical judgment of the responsible physician. This will be appropriately documented.

Upon completion of this review, the SRC will determine if the study enrollment or study dosing should be interrupted or if study enrollment and study dosing may continue according to the protocol. Should the trial not be stopped at this time point, the final analysis would need to account for the number of interim analyses that were conducted. Therefore, we will use the O'Brien and Flemming type spending function to preserve the overall Type 1 error. This will

Version: 7.0

Version: 7.0 18 May 2021

allow for stopping the trial earlier should the intervention arm be shown to be superior at an interim analysis.

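### Sections 8.5.1 and 8.10.2 disagree on whether a worsened Grade 3 or 4 laboratory result that is silent and needs no action is an adverse event

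*Protocol*

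**What the plan says.** Protocol Section 8.5.1, which defines an adverse event, sets a necessary condition for laboratory findings: "Abnormal laboratory values or test results constitute AEs only if they induce clinical signs or symptoms or require investigation or therapy". It then equates that condition with clinical significance ("i.e., are considered to be clinically significant"). Grade plays no part in the rule.

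Protocol Section 8.10.2, on laboratory abnormalities, works by grade. After dosing starts, "all grade 3 and 4 clinical laboratory results that represent an increase in severity from baseline will be reported as AEs". Clinical judgement enters only for the lower grades: "A grade 1 or 2 clinical laboratory abnormality should be reported as an AE only if it is considered clinically significant by the investigator".

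Neither section refers to the other, and the protocol does not say which one governs.

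Adverse events are the first primary safety endpoint in Section 1.2. Section 6.2.6 says how they are counted: "The number and percentage of participants with treatment-emergent AEs will be tabulated by system organ class (SOC) and preferred term". The fourth primary safety endpoint in Section 1.2 is a separate one, "Safety laboratory assessments", with its own numerical limits for haemoglobin, platelets, transaminases, amylase and lipase. Sections 8.6 and 8.7 ask the investigator to rate relationship to study drug and severity grade for adverse events.

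**The concern.** One section makes a clinical consequence necessary before a laboratory value can be an adverse event. The other makes grade and worsening sufficient. Both cannot hold for a severe result with no clinical consequence. An example is an inpatient whose lipase rises to Grade 3 without symptoms while the team merely carries on with routine bloods. One site could enter this as an adverse event and another could leave it out, and each could cite the protocol.

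What is at stake is the count behind a primary safety endpoint, and with it the blinded safety summaries planned for the interim looks in Section 9.2. A second consequence is that a result not entered as an adverse event carries no causality or grade assessment that Sections 8.6 and 8.7 require. The choice is made when the site completes the case report form, so an analysis plan cannot fully repair it later: the missing entry and the missing assessment would not be in the data.

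**Working it through.** The plan gives no figure on this point, so there is none to reproduce. The check sets the two rules side by side, case by case.

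Inputs:
- Rule A (Section 8.5.1): the result is an adverse event only if it is clinically significant, meaning that it is symptomatic or needs work-up or treatment.
- Rule B (Section 8.10.2): the result is an adverse event if it is Grade 3 or 4 and worse than at baseline, or if it is Grade 1 or 2 and clinically significant.
- Assumption: clinical significance means the same in both sections, as the gloss in Section 8.5.1 suggests. All results in the table are taken to have worsened from baseline.

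| Grade | Clinically significant? | Rule A | Rule B | Agree? |
|---|---|---|---|---|
| 1 | no | not an AE | not an AE | yes |
| 1 | yes | AE | AE | yes |
| 2 | no | not an AE | not an AE | yes |
| 2 | yes | AE | AE | yes |
| 3 | no | not an AE | AE | **no** |
| 3 | yes | AE | AE | yes |
| 4 | no | not an AE | AE | **no** |
| 4 | yes | AE | AE | yes |

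The rules agree in 6 of 8 combinations and conflict in 2. Both conflicts are severe results without clinical significance. Absence of symptoms alone does not create the conflict: an asymptomatic Grade 3 or 4 value that prompts work-up or treatment is an adverse event under both rules.

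What depends on the choice:
- The adverse-event tabulation in Section 6.2.6 changes, because the participant is counted under Rule B and not under Rule A.
- The relationship and grade assessments in Sections 8.6 and 8.7 are required under Rule B and not under Rule A.
- The laboratory endpoint in Section 1.2 does not change, because the blood result is collected under the schedule in Section 7.1 whichever rule the site applies.

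On size, Section 6.1 plans on about 14 participants in a dose group. One participant counted under one rule and not the other moves a percentage in that group by 1/14 = 7.1 points. How many such participants there would be is not stated and cannot be derived from the document.

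**The case against.** The strongest reply is that Section 8.10.2 is the specific operating instruction for laboratory results and Section 8.5.1 only the general definition, so the specific text prevails and many sites would follow it. That is a sensible reading, but the protocol does not state it. A definition worded as a necessary condition does not yield to a later section without a cross-reference. With two named sites and up to five more, uniform practice cannot be assumed.

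A second reply is that nothing is lost, since laboratory safety is a primary endpoint in its own right. This stands in part. A reader might infer that the result goes unrecorded or drops out of primary safety altogether. It does not: the value stays in the laboratory data and under the fourth endpoint. Only its status as an adverse event, and what the protocol attaches to that status, is in doubt.

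A reader might also infer that the study-level stopping rule breaks down. The documents do not support that. The criterion reads "Two participants with a Grade 3 or higher lab toxicity for the same parameter associated with the study product" and turns on laboratory toxicity, not on adverse-event status. Another criterion in Section 9.2 lets the safety review committee judge patterns of laboratory events itself. Under Section 9.1 the committee sees blinded safety data and can ask for further analyses, and its procedures sit in a charter that is not shown. What survives is narrower: for a value left off the adverse-event form, the protocol requires no investigator attribution that the committee could draw on.

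Finally, the trial is double-blind, so a site chooses its reading without knowing the arm. The ambiguity affects the level and consistency of reporting; a bias between arms is not shown. Attaching a percentage does not help either. Assuming that 10 to 30% of participants have such a result gives 1 to 4 of 14, or 7 to 29 points, which is the assumption restated in whole participants.

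**Conclusion.** The contradiction is real and the text is wrong as written, but it is confined to Grade 3 or 4 results that worsened from baseline, caused no symptoms and called for no work-up or treatment. For those results the first primary safety endpoint has two incompatible counting rules, and causality and grade assessment is required under one rule only.

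The size cannot be quantified from the documents. It depends on how often such results occur, on how broadly sites read the need for investigation (the broader the reading, the smaller the conflict), and on how sites divide between the two sections. The conclusion rests on the wording alone and on the absence of any rule of precedence. To describe the sections as opposite in general would go too far, since they agree on Grades 1 and 2 and on every clinically significant result.

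**What to change.** Reconcile the two sections so that one rule governs at all sites. The simplest way is to replace the laboratory sentence in Section 8.5.1 with a cross-reference, for example: *Laboratory abnormalities are AEs as set out in Section 8.10.2.* Section 8.10.2 can stay as it is. Sites should be told of the change, and results already reported should be checked against the single rule.

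If the sponsor also wants the safety review committee's work under Section 9.2 not to depend on site adverse-event entry, a list of Grade 3 or higher results can be drawn from the laboratory data. It should be pooled and blinded, not split by arm, because Section 9.1 has site investigators and the medical monitor reviewing blinded data.

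The cost is one sentence, a short notice to sites, and slightly more adverse-event entries in a sick inpatient population. The optional list uses data that are already collected.

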8.5.2. Serious Adverse Event

An SAE is an undesirable sign, symptom or medical condition which:

- Results in death
- Is life threatening (defined as an event in which the participant was at risk of death at the time of the event; it does not refer to an event which hypothetically might have caused death if it were more severe)
- Requires inpatient hospitalization or causes prolongation of existing hospitalization (see note below for exceptions)
- Results in persistent or significant disability/incapacity
- Is a congenital anomaly/birth defect (note: reports of congenital anomalies/birth defects must also be reported on the Pregnancy Supplemental Form, although participants must have a negative pregnancy test prior to therapy and use at least 2 forms of non-hormonal contraception. All participants (men and women) must state that they will use 2 forms of contraception during the study and for 4 days after completion of EIDD-2801 dosing in female participants and for 4 days after completion of EIDD-2801 dosing in female partners of male participants.
- Is an important medical event (defined as a medical event(s) that may not be immediately life-threatening or result in death or hospitalization but, based upon appropriate medical and scientific judgment, may jeopardize the participant or may require intervention [e.g., medical, surgical] to prevent one of the other serious outcomes listed in the definition above.). Examples of such events include, but are not limited to, intensive treatment in an emergency room or at home for allergic bronchospasm; blood dyscrasias or convulsions that do not result in hospitalization.)

Events **not** considered to be SAEs are hospitalizations for the:

- Admissions as per protocol for a planned medical/surgical procedure or to facilitate a procedure.
- Routine health assessment requiring admission for baseline/trending of health status (e.g., routine colonoscopy).
- Medical/surgical admission for purpose other than remedying ill health state and was
 planned prior to entry into the study. Appropriate documentation is required in these
 cases.
- Admission encountered for another life circumstance that carries no bearing on health status and requires no medical/surgical intervention (e.g., lack of housing, economic inadequacy, care-giver respite, family circumstances, administrative).

Version: 7.0

- Version: 7.0 18 May 2021
- Escalation of care that is considered part of the disease progression of COVID-19
 (including but not limited to need for escalation in supplemental oxygen, need for
 mechanical ventilation, need for intubation, admission to the ICU, cytokine release
 syndrome [defined by an elevation in IL-6 and CRP levels], thromboembolic events) will
 not be collected as SAE.
- Pregnancies will be reported using the SAE reporting guidelines for expedited reports (Section 8.10.4).

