8.10.3. Serious Adverse Event Reporting

All SAEs (including deaths) occurring from the first dose of the study drug through the 28 day End-of-Study telephone call will be collected and recorded on the Adverse Event Case Report Form (CRF).

The PI or clinical site personnel should notify of all SAEs, regardless of relationship to the investigational drug, within 24 hours of clinical site personnel becoming aware of the event. The PI (or designee) will provide the initial notification by sending a completed SAE form which must include the PI's (or designee's) assessment of the relationship of the event to investigational drug and must be signed by the PI. Follow-up information, or new information regarding an ongoing SAE, must be provided promptly to at or via fax.

Version: 7.0

The SAE Form will collect data surrounding the event (e.g., the nature of the symptom[s], time of onset in relation to initiation of therapy, duration, intensity, and whether or not therapy was interrupted or discontinued). The Investigator's assessment of the probable cause of the event will also be included. In addition, relevant medical history, concomitant medications, laboratory and diagnostic tests reports, and procedures as well as all pertinent medical information related to the event will also be collected.

SAEs will be reported to each participating site's IRB per institutional guidelines by the PI.

After the initial SAE report, the investigator is required to proactively follow each participant and provide further information regarding the participant's condition.

All AE(s) and SAE(s) will be followed until one of the following conditions is met:

- Resolution
- The condition stabilizes
- The event is otherwise explained
- The participant is lost to follow-up
- Death

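### The SAE exclusion for COVID-19 progression removes serious events, above all thromboembolism and cytokine release syndrome, from the SAE endpoint and from SAE-triggered oversight

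*Protocol*

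**What the plan says.** Protocol Section 1.2 sets the primary safety objective: "To evaluate the safety of treatment with EIDD-2801 in participants diagnosed with COVID-19". AEs and SAEs are listed as separate primary safety endpoints.

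Section 8.5.2 defines an SAE by the usual criteria, including life-threatening events and prolonged hospitalization. It then lists what does not count. One entry is "Escalation of care that is considered part of the disease progression of COVID-19". After oxygen escalation, its examples run "mechanical ventilation, need for intubation, admission to the ICU, cytokine release", then "syndrome [defined by an elevation in IL-6 and CRP levels], thromboembolic events) will", and the sentence ends "not be collected as SAE". The examples are expressly not exhaustive.

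Section 8.10.3 requires "All SAEs (including deaths) occurring from the first dose of the study drug" through Day 28 to be recorded, with notification by the site within 24 hours. In Section 9.2, stopping criterion III is "A trend of unexpected SAEs related to the study product".

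**The concern.** The exclusion acts on collection, not merely on expedited reporting. It turns on a judgement, event by event, that an escalation belongs to the disease. Nothing says who makes that judgement or by what criteria.

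In hospitalized COVID-19 patients that judgement is hard to make from a single case. Section 3.1 itself notes the raised risk of venous thrombosis in this population, so almost any clot could be put down to the disease. The randomized comparison is what can separate drug from disease, and the exclusion is applied before that comparison is made. If the drug aggravated COVID-19 or promoted thrombosis, the resulting events would resemble progression and could leave the SAE data.

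**Working it through.** **1. The exclusion against the protocol's own definitions.**

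- In 8.5.2 the pointer to exceptions is attached only to the hospitalization criterion, and the list of exceptions is introduced as a list of hospitalizations. The life-threatening and important-medical-event criteria carry no such pointer. An intubation or a pulmonary embolism can therefore be an SAE by one criterion and excluded by the list.
- Thromboembolism and cytokine release syndrome are diagnoses, not escalations of care, yet they stand in the list of escalations.
- Section 8.8 says no event is treated as expected for safety reporting, while 8.5.2 sets a class of events aside as the expected course of disease.
- Section 8.10.1 says AEs that become serious are to be reported as SAEs, without exception.

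**2. What depends on SAE status.**

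| Element | Needs SAE status? | Effect of the exclusion |
|---|---|---|
| SAE primary safety endpoint (1.2) | Yes | Events drop out |
| Serious-AE summary (6.2.6) | Yes | Events drop out |
| 24-hour notification (8.10.3) | Yes | Not triggered |
| 24-48 h review of grade 4-5 SAEs (9.1) | Yes | Not triggered |
| Stopping criterion III (9.2) | Yes, and unexpected and related | Loses input |
| Interim SAE incidence and risk difference by arm (9.2) | Yes | Events drop out |
| AE primary safety endpoint (1.2, 8.5.1, 8.10) | No | Kept if recorded as AEs |
| Twice-monthly protocol team review (9.1) | No, covers all AEs | Kept if recorded as AEs |
| Stopping criterion V (9.2) | No | Kept |
| Oxygen, ventilation and ICU days, peak WHO stage, death (1.4) | No | Kept |

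**3. Where the remaining cover is thinnest.** The clinical data extracted from charts (7.1, inpatient footnote j) are hospital days, oxygen need, ICU stay, ventilation, death and symptoms. Thromboembolic events and cytokine release syndrome are not among them, nor are they secondary or exploratory clinical endpoints (1.4, 1.6). Cytokine release syndrome is defined by raised IL-6 and CRP with no thresholds. The listed study laboratory tests are CBC, CMP with amylase and lipase, and urinalysis, so CRP is not among them. IL-6 is scheduled on Days 1 and 5 and on Day 19 (4.5) or Day 28 (7.1, outpatient footnote c).

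**4. Illustration of size.** The protocol states no SAE or escalation rate. Its only power figure concerns the virologic endpoint: 80% against 20% detectable, 14 per arm, Fisher's exact test, alpha 0.05, 83% power. Exact enumeration, two-sided, gives 83.7%, so that figure reproduces. The same routine is used below.

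Assumptions not in the protocol: escalation in 20% on placebo and 40% on active; other SAEs in 5% of each arm, in different participants; a share *s* of escalations excluded, equal in both arms.

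- Placebo SAE rate = 0.05 + 0.20(1 − *s*)
- Active SAE rate = 0.05 + 0.40(1 − *s*)
- Difference = 0.20(1 − *s*)

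Arm sizes: 14 v 14 is the minimum in Section 6.1. Every study part allocates one third to placebo, so 84 participants give 84/3 = 28 placebo and 56 active.

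| *s* | Placebo | Active | Difference | Power, 14 v 14 | Power, 28 v 56 |
|---|---|---|---|---|---|
| 0 | 25% | 45% | 20 points | 11.3% | 37.5% |
| 0.5 | 15% | 25% | 10 points | 4.0% | 13.7% |
| 0.9 | 7% | 9% | 2 points | 0.3% | 2.7% |
| 1 | 5% | 5% | 0 | 0.0% | 2.2% |

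The SAE difference shrinks in proportion to the share excluded. The first row also shows that the SAE comparison has little power at this size even when nothing is excluded.

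**The case against.** A reader might infer that the primary safety comparison cannot show drug-induced worsening at all. The protocol does not support that. AEs are a separate primary safety endpoint. Section 8.5.1 defines them regardless of relatedness and includes worsening of existing disease, 8.10 collects them from first dose, and 6.2.6 tabulates them by term and severity. The exclusion is worded for SAEs only. Deaths remain SAEs under 8.10.3. Oxygen, ventilation, ICU stay and WHO stage can be compared by arm with no causality judgement.

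It would likewise be wrong to say that thromboembolism and cytokine release syndrome have no other endpoint, since both can be recorded as AEs and IL-6 change is an exploratory endpoint. The twice-monthly review is not lost either, because it covers all AEs. Nor does the text say that the investigator decides; it uses the passive and names nobody.

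Three further points are fair. Reference to all SAEs in 8.10.3 can be read as SAEs as defined in 8.5.2, so that section alone is not a contradiction. Treatment is double-blind, so the judgement should not favour an arm through knowledge of assignment; the expected effect is dilution. Stopping criterion V and the study physician's judgement also remain open routes to a halt.

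What survives is that AE capture of the excluded events is left to inference from general text, the SAE-specific safeguards do not see them, and ventilation and ICU days as efficacy endpoints trigger no prompt safety review. Section 8.6 sharpens this for criterion III: an event counts as related only if no other cause can be identified, and COVID-19 is always a candidate cause here.

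**Conclusion.** The point holds in a limited form. On an undefined judgement, Section 8.5.2 removes events that can be life-threatening from one of the primary safety endpoints and from the SAE-triggered parts of oversight. General AE capture and the secondary clinical endpoints reduce the loss for oxygen, ventilation and ICU care. They reduce it least for thromboembolism and cytokine release syndrome.

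The size cannot be fixed from the protocol. The fall from 20 points to 10, 2 or 0 rests wholly on the assumed rates and excluded shares. Since significance would be unlikely anyway, and Section 8.1 says the trial is not powered for clinical outcomes, the harm lies in a visible imbalance being diluted or missed by those watching for it, rather than in a lost test. No figure in the protocol changes. This is a worthwhile, inexpensive correction, not a flaw that invalidates the safety analysis.

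**What to change.** Amend 8.5.2 and reconcile it with 8.8, 8.10.1 and 8.10.3:

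- Record every event meeting a seriousness criterion in the CRF, whatever the view on progression, with a flag for anticipated COVID-19 progression.
- State who sets the flag and on what criteria, including what counts as cytokine release syndrome given the tests actually scheduled.
- Exempt flagged events only from individual expedited reports.
- Tabulate serious events by arm with and without flagged events.
- Include flagged events in the aggregate data that the safety review committee sees.

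The cost is amendment wording, one CRF flag, one additional table and more event forms for sites. The waiver of individual expedited reports limits that burden.
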